4.3 Inclusion Criteria

- a) Adult males or females (18 to 64 years)
- b) DSM 5 diagnosis of schizophrenia or schizoaffective disorder
- c) Ability to provide informed written consent
- d) PANSS total score ≥ 70 and at least 2 positive symptom subscale items (i.e., delusions, conceptual disorganization, hallucinatory behavior, excitement, grandiosity, suspiciousness/persecution, hostility and unusual thought content) scoring ≥ 4 , or one of these items scoring ≥ 5 , on a scale ranging from 1 = absent to 7 = extreme.
- e) Receiving anti-psychotic medications for ≥ 4 weeks
- f) evidence of a positive symptom exacerbation during the year prior to study entry. Evidence of an exacerbation may be identified from medical records; by a need to increase the individual's psychiatric medication; by a need for an increased level of care; or through a history from the participant's treating clinician.
- g) For women of child bearing age, a negative serum pregnancy test at screening.

4.4 Exclusion Criteria

- a) Testing positive for illicit substances (positivity to marijuana or opioids will be assessed on a case by case basis due to the long elimination half life in the urine of marijuana and the use of opioids for various pain disorders, , caffeine and nicotine are excepted)
- b) Receiving pharmacological treatment for addictions (naltrexone, suboxone, acamprosate, others) will be reviewed on a case by case basis
- c) Seriously unstable medical illnesses
- d) Pregnant or breast feeding women
- e) Known allergy or history of serious adverse event with WSE
- f) Subjects who may require imminent hospitalization (examples: suicidal or aggressive behavior)
- g) Currently receiving antibiotics, anti-viral, or anti-parasitic medications
- h) Currently receiving immunosuppressive medications (e.g. oral scheduled corticosteroids, chemotherapy or transplantation or HIV/AIDS associated drugs).

5.0 Study Treatments

Study drug will be dispensed by the research pharmacies at UCLA and MPRC. All unused study medication and empty bottles will be returned at each office visit.

During each office visit, the participant will be asked about symptoms, any side effects and questions relating to his/her health in general. If any side-effects emerge, the dosage can be decreased or the titration can be stopped. Participants who cannot tolerate at least 500 mg/day of Sensoril® will be discontinued from the study. Participants who experience side-effects after reaching the higher dose (1000 mg/day) can be tapered to a minimum of 500 mg/day of Sensoril®.

Placebo capsules made of gelatin will be provided by Natreon Inc., who will also provide Sensoril® capsules, each of 250 mg strength. Details of the Sensoril® and placebo capsules can be found in the **section 5.4** (drug supplies)

5.1 Allocation to Treatment

Sensoril® (or placebo) will be administered using a random 1:1 assignment starting at a dose of 500 mg/day (1 capsule of 250 mg strength twice a day). Then the study treatment dosage will increase in the second week to the target of 1000 mg/day; (2 capsules of 250 mg strength twice a day) as an adjunct to existing antipsychotic treatment. The dose of 1000 mg per day (or less, i.e., a minimum of 500 mg if tolerability is an issue) will be continued for the rest of the study. The randomization numbers will be computer generated and the blinded assignments maintained in the pharmacies.

5.2 Breaking the Blind

Blinding will be maintained by the dispensing pharmacists at the UCLA and MPRC research pharmacies and so the clinician team and study participants will remain blind to treatment assignment throughout the tenure of the study.

If unintentionally or intentionally (see next paragraph) the blind is “broken,” data collection will be stopped at that point for that individual participant. A case by case basis for completion of study procedures (i.e., even if efficacy data collection is stopped, safety data collection will

continue), if the participant would prefer to complete the study and the investigative team sees no reason that may harm the participant or the study goals, study completion may be permissible based on discussion with the Data and Safety Monitoring Board (DSMB).

If unblinding is absolutely necessary, the study PI will contact the research pharmacist to obtain the treatment assignment information and notify the appropriate entities as soon as feasible. (e.g. DSMB, IRB)

After completion of the entire study and after the data bases are “locked” and statistical analyses have been completed, if participants would like to know their treatment assignment, the research team will provide them that information.

Statistical analyses of primary and secondary outcomes will be carried out “blind” to treatment assignment. The treatment assignment to Sensoril® or placebo will be revealed upon completion of the main statistical analyses.

5.3 Treatment Adherence/Study Compliance

Once the dispensing of the medication begins, adherence will be recorded by the study coordinator on log sheets in the research binder during each visit. Adherence will be based on discussions with participant and returned capsule counts. Participants who withdraw consent or whose clinical status worsens to prevent continuation in the study will be withdrawn and stabilized under standard clinical care conditions. There is no open continuation phase in this study. Participants will be counseled about this issue prior to initiating the study and advised

that Sensoril® may be obtained over the counter or via the internet through a general nutritional supplement outlet.

Participants who are found to be non-compliant with daily dosing of Sensoril®/placebo for a period of 7 consecutive days during the 12 week study period, or are otherwise found to be significantly non-compliant with study procedures and/or investigator instructions may be withdrawn from study participation.

If there are more dropouts than anticipated and other considerations (e.g. budget, etc.) permit more participants to be recruited, we may modify our protocol and consent and request the IRB to recruit more participants until we have 66 participants with evaluable primary efficacy data.

6. Drug Supplies

6.1. Formulation and Packaging

Placebo capsules made of gelatin will be provided by Natreon Inc., who will also provide Sensoril® capsules, each containing 250mg of standardized WSE extract. The inactive ingredients in the Sensoril® capsule will comprise microcrystalline cellulose NF 102 – 50 mg, croscarmellose Sodium NF – 10 mg, silicon Dioxide, Fumed NF (Cab-O-sil) – 3mg, magnesium sterate, NF – 3mg. The placebo capsules will only contain the inactive ingredients, and the fill weights of the Sensoril and placebo capsules will be the same; except the placebo capsules will not contain WSE extract. The placebo and Sensoril® capsules will be in coded hard-gelatin capsules, identical in color (opaque white), size, texture and shape. Based on our previous

clinical trial experience, to mask the smell, cloth pouches which are closed and contain Sensoril® powder will be placed alongside the placebo capsules and the smell will permeate the placebo capsules. The Sensoril® or Placebo capsules will have a “spice-like” odor. For individual participant dispensing-please see next section 5.4.b.

6.2. Drug Administration

The study medicine (Sensoril® or Placebo) will be prescribed as follows: 1 study capsule 250mg p.o. BID (total daily dose = 500mg) week 1; and 500mg p.o. BID (total daily dose = 1000mg) starting the second week to the end of the study. A lower dosage is permissible for tolerability issues; however, those participants unable to tolerate at least 500 mg/day will be discontinued from the study.

6.2. Concomitant Medications

Furthermore, medications for hypertension, diabetes mellitus and others for various medical conditions, can continue as usual. Physicians and clinicians involved in the routine psychiatric/medical care of the participant will continue to see them as usual.

Participants will be requested to let the research staff/prescribing study physician know prior to taking any new medication (including over-the-counter drugs and herbal supplements) during their participation in this clinical investigation.

7. Study Procedures

7.1. All participants will receive a screening visit to determine study eligibility. Diagnosis will be verified by history, chart review and discussion with the clinicians of the potential participant. The consent form will take into consideration that such permission to contact the treating clinician is warranted not only to affirm the diagnosis, but that lack of imminent suicidal or aggressive behavior or hospitalization can also be verified. The diagnosis of schizophrenia or schizoaffective disorder and comorbid Axis-I disorders will be affirmed using the SCID. Initially eligible participants will then have a review of their medical history, have their blood pressure, pulse, weight and height recorded; (including a serum pregnancy test for women of child-bearing potential), EKG and laboratory assessments.

The specifics of the inclusion and exclusion criteria are provided in the Participant Selection section.

Participants with **co-morbid disorders** will be allowed to participate provided the co-morbid condition was diagnosed more than 3 months ago, and no pharmacological treatments for these disorders were changed in the 3 month period prior to screening. This 3-month period will permit participants whose co-morbid conditions are stable but not the current focus of treatment to enter the study. Participants who have previously experienced serious side-effects with WSE will be excluded.

7.2. Study Treatments, Assessments and Follow up

After all screening procedures have been completed and reviewed and the participant remains eligible for the study, the participant will receive either Sensoril® or placebo at visit 2. The

participant will get one of these medicines by chance (like flipping a coin), and have a 1 in 2 chance of getting either Sensoril® or placebo. The medicine is packaged identically so that it is not possible to tell which is Sensoril® or which is placebo. The medicine will be given to the participant as capsules, and is taken by mouth. Starting at 1 capsule twice daily, the medicine (or placebo) will be increased to 2 capsules twice daily a week later, unless the participant is experiencing side effects. Neither the participant, or the doctor or the research staff will know if the participant is receiving Sensoril® or placebo.

If any tolerability issues emerge, further titration of study medicines can be stopped at a minimum 500 mg/day. If dosage has been increased to 1000 mg/day it can be decreased to 500 mg/day for side-effects.

Details of procedures at each visit (Visit 1 to 8) are described in the schedule of events (**3.2.c.**). Psychopathology ratings (details of the scales were described in **Section 3.2.d** earlier) are briefly mentioned in section 7.1.a. Safety assessments will include determination of side effects at each visit, and depending on the side effects, further clinical action will be undertaken. Laboratory measures at baseline and end point will provide more safety data as will careful monitoring of physical and psychological status at each visit.

If the participant would like to know the treatment assignment at the end of the data analyses and if a contact address or phone number is left with research staff, we will attempt to notify them of their treatment assignment during the study.

7.3. Efficacy and Safety Assessments

As noted in the Schedule of Events table, psychopathology (PANSS, CGI) and stress (PSS) scales will be assessed at every visit and will form the measurements required for affirming the primary efficacy outcomes, and will inform future studies about the size of the WSE treatment effects. These scales will also assist in monitoring psychopathology and stress as safety concerns.

Psychotropic Medications

These medications are listed in the database by name, daily dosage, start and stop dates. This will permit coding of increases (or decreases) in doses of existing medications, stopping of existing medications (e.g. stopping an existing antipsychotic and starting a new one), etc. Further discussion of the data analysis is provided in section 9.1.c – Psychotropic Medication End Points

Safety Assessments

During the screening process, a review of the medical history, recording of vital signs, laboratory and EKG assessments will provide safety data to the PI and research staff, and help them assess suitability of the subject for the study.

Side-effects will be monitored at each visit, by asking an open ended question and following up with the MPRC Side Effect Checklist. Based on the nature of the side effects, these may be attended to by either reducing the dosage, discontinuing study capsules, with follow-up

laboratory and/or physical examinations, or consultations, until resolution occurs. Recording of vital signs, the use of psychopathology and stress rating scales will further assist in evaluating safety of participating participants.

7.4. Data and Safety Monitoring Board (DSMB)

The MPRC has established a Data and Safety Monitoring Board (DSMB), which is comprised of two psychiatrists, a statistician, a pharmacist, and a community representative. The psychiatrists are experts in the clinical treatment of people with schizophrenia. None of the DSMB members reviewing this study will be investigators on the proposed project; however, [name] serves as a non-voting member of the DSMB to assist in the monitoring of all MPRC trials. The DSMB will be charged with the following responsibilities: 1) to review the proposed protocol; 2) to monitor study progress and the occurrence of side effects/adverse events, and serious adverse events throughout the course of the study; and 3) to review with [name], the statistician for the project, the study data management system. The DSMB will review reports on protocol progress, side effects and adverse events at least once a year. In addition, all serious adverse events (SAEs) will be reported to the DSMB, [name], and the University of Maryland School of Medicine IRB. [name] will receive all SAE reports within 24 hours of their occurrence. The DSMB and University of Maryland School of Medicine IRB will receive the reports within 48 hours. If the incidence of any side effect/adverse event is 25% or more or any SAE occurs in excess in either treatment group, then the DSMB will notify the P.I.s. The P.I.s and DSMB will determine whether possible protocol modifications are required to minimize the further occurrence of such events.

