All individuals (P.I. and research staff) involved with the study will attempt to meet weekly throughout the duration of the research study to discuss and monitor confidentiality, data, recruitment and adverse events, including clinical outcomes relating to the participants in the study. At the weekly research meetings, the P.I. and all study personnel will be apprised of new developments relating to the study participants. Any unanticipated problems and unanticipated, serious adverse events felt to be possibly related or related to the research interventions will be reported to the University of Maryland and UCLA IRB's in accordance with the IRB's reporting requirements. Adverse events and reports from the data and safety monitoring will be reported to the IRB sooner if it changes the risk to benefit ratio of the protocol. In accordance with IRB adverse event reporting these will be in addition to the yearly summaries. A summary of all the unanticipated adverse events observed during the course of the study in a twelve-month period will be reported to the IRB at the time of the annual review.

All research data is recorded on Case Report Forms that will be stored in a locked file cabinet in study personnel's office. The research forms will not include any form of identifying information. ID numbers rather than subject identifiers are used to record information on computer databases which are protected by firewalls and only authorized personnel with user id and passwords are permitted to enter and view the data.

10. Data Handling and Record-Keeping

10.1. Data recording/Case Report Forms A Case Report Form will be completed for each subject enrolled into the clinical study. The investigator-sponsor will review, approve and sign/date each completed CRF; the investigator-sponsor's signature serving as attestation of the investigator-sponsor's responsibility for ensuring that all clinical and laboratory data entered on the CRF are complete, accurate and authentic. We will make all efforts to collect all data points associated with this research. Research staff will utilize various sources, including electronic medical record information for verification purposes, when available.

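### Section 7.4 has the DSMB send the blinded P.I.s a notice that is between-arm information at least for SAEs in excess, with no limit on its content or on who sees it

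*Combined protocol and SAP*

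**What the plan says.** Section 7.4 gives the trigger: "If the incidence of any side effect/adverse event is 25% or more or any SAE occurs in excess in either treatment group". Once it is met, notification is mandatory ("then the DSMB will notify the P.I.s") and the decision is shared: "The P.I.s and DSMB will determine whether possible protocol modifications are required to minimize the further occurrence of such events".

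Section 5.2 says that "the clinician team and study participants will remain blind to treatment assignment throughout the tenure of the study". Section 7.2 extends this to the doctor and research staff: "Neither the participant, or the doctor or the research staff will know if the participant is receiving" Sensoril or placebo. The P.I. is blind by default, because if unblinding is unavoidable "the study PI will contact the research pharmacist to obtain the treatment assignment information".

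Section 9 describes meetings, weekly where possible, on data, adverse events and clinical outcomes, at which "the P.I. and all study personnel will be apprised of new developments relating to the study participants".

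The plan has no closed DSMB session, no coded arms, no rule on the content of the notice, and no barrier between the P.I.s and the raters.

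**The concern.** A notice that SAEs are in excess in one group is a statement about a difference between arms. It goes to people who are meant to be blind, and they then help decide what to do about it. In a comparison of active with placebo, the natural guess is that the higher group is the active one. Staff already know who has which event, because section 7.3 has side effects asked about at every visit, with a checklist.

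The primary outcome, PANSS total, is scored by an interviewer, and the CGI is a clinical impression (section 3.5). Guesses about assignment could colour those ratings, as well as decisions on dose reduction and retention. The protocol itself treats partial unblinding as worth preventing: section 6.1 masks the odour of the capsules.

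**Working it through.** **1. Scope of the trigger.** In 7.4 the words on treatment group come at the end of the sentence. They certainly govern the SAE clause. They may or may not govern the 25% clause.

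- SAE clause: by arm and comparative on any reading. What counts as an excess has no number or test.
- 25% clause, by-arm reading: an absolute level in an arm. An event at 30% in both arms would meet it, so the notice alone does not say that the arms differ.
- 25% clause, pooled reading: it tells the P.I.s nothing they could not count from their own case records.

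**2. Arm size.** Section 8.6 gives 33 per arm for effect size 0.83. A two-sample t-test at alpha 0.05 gives power 0.955 one-tailed and 0.913 two-tailed at 33 per arm, against the stated 0.95 and 0.90. All eight cells of the table reproduce. The 25% level has no derivation to check. In an arm of 33 it means 0.25 × 33 = 8.25, so 9 participants. The documents give no adverse event rates, so every rate below is an assumption.

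**3. What a notice lets staff infer if the drug causes the event.** Assume 30% on active, 10% on placebo, and the 25% counted by arm.

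- P(X ≥ 9 | 33, 0.30) = 0.696 and P(X ≥ 9 | 33, 0.10) = 0.004.
- At least one arm: 1 − (1 − 0.696)(1 − 0.004) = 0.70.
- Given that, the mean share of participants with the event who are on active is 0.78.

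The share without conditioning on the trigger is 0.30 / (0.30 + 0.10) = 0.75. The high share therefore comes mainly from the assumed drug effect. What the notice adds is to draw staff's attention to that event.

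**4. How often a notice is sent if the drug has no effect on the event.** Let q = P(X ≥ 9 | 33, p), with the same p in both arms and the 25% counted by arm. One event reaches 25% in at least one arm with probability 1 − (1 − q)². For any of 10 independent events it is 1 − (1 − q)²⁰.

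| True rate p | q | One event, either arm | Any of 10 events |
|---|---|---|---|
| 10% | 0.004 | 0.01 | 0.08 |
| 15% | 0.049 | 0.10 | 0.64 |
| 20% | 0.200 | 0.36 | 0.99 |

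Smaller arms at an early review usually trigger more easily. With 10 per arm, 3 participants reach 25%, and the one-event figures are 0.14, 0.33 and 0.54.

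**5. The SAE clause.** If any difference in counts were treated as an excess, two arms of 33 with the same SAE rate would differ with probability 1 − Σ P(X = x)². That is 0.60, 0.77 and 0.83 at assumed rates of 2%, 5% and 10%. The definition in 7.5 is broad, since any unexpected adverse experience counts as an SAE.

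**The case against.** The strongest case against the point is that it builds on silence. Four parts of it stand.

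- A reader might infer that the notice names the arm or reveals who is on active. Section 7.4 says neither, and assignments stay with the pharmacists under 5.2.
- A reader might infer that the 25% rule reports a difference between arms. It is an absolute level, and it may be pooled. Only the SAE clause is comparative.
- A reader might infer that the plan passes the notice to the raters. Section 9 speaks of developments concerning participants and does not mention DSMB notices, and nothing says that the P.I.s rate the PANSS. The most that can be said is that no rule prevents it.
- A reader might take 0.99 as the chance that the blind is compromised. It is the chance of a notice when the drug does not affect the events. In that case, with the arm unnamed, a participant with the event is equally likely to be in either arm. It also assumes ten independent events, all at 20%. At 10% the figure is 0.08.

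Two more points are fair. The P.I.s need to be able to act on safety. DSMB review is guaranteed only once a year, so a late notice could come after many ratings are done.

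What the objection does not remove is the SAE clause. There the plan requires a by-arm signal to go to blinded investigators and gives them a share in the decision.

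**Conclusion.** The point holds in a limited form. For SAEs in excess, 7.4 obliges the DSMB to give between-arm information to P.I.s whom the rest of the protocol keeps blind. The 25% clause does so by arm only on one reading of the sentence. Neither clause is shown to disclose individual assignments.

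The harm is conditional. It arises if the drug causes the event and the information reaches people who rate or manage participants. The 0.70 and 78% illustrate that case under assumed rates. The probabilities for equal rates show only how readily a notice could be sent. The documents give no basis for a figure on bias in the PANSS, so none is claimed. This is a cheap improvement to make, not a reason to doubt the design.

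**What to change.** Revise the trigger paragraph in 7.4 so that it agrees with 5.2 and 7.2:

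- State whether the 25% level is pooled or counted by arm, and what the board will treat as an excess of SAEs.
- Have the DSMB review by-arm data and form its decision in closed session.
- Send the P.I.s pooled adverse event counts and a recommendation (continue, modify or stop), without by-arm incidence and without saying that one arm met the trigger. Allow an exception where the DSMB judges disclosure necessary for participant safety.
- Keep any by-arm information disclosed under that exception from the PANSS and CGI raters.

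The cost is one paragraph and a closed report by the DSMB statistician. The P.I.s would have less detail when acting on a recommendation. A recommendation aimed at one event may still hint that the board saw a signal, so the change reduces the leak and does not remove it.
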